14 SAFETY ANALYSES

14.1 Adverse Events

Adverse events will be coded using Medical Dictionary for Regulatory Activities (MedDRA) version 26.1.

Treatment-emergent adverse events (TEAEs) are defined as any adverse events that occur during or after the Day 1 injections, or any adverse events that are continuous from the screening but worsen during or after the Day 1 injections.

Ocular and non-ocular TEAEs will be summarized separately. Summary of ocular TEAEs will be separated by study eye and non-study eye.

An overall summary including the number of events and the number and percentage of subjects who experienced at least one TEAE will be presented by treatment group and overall. The overall summary will also include at least one serious TEAE, treatment-related TEAE, treatment-related serious TEAE, TEAE leading to subject discontinuation from the study, and TEAE leading to death.

TEAEs will be summarized by System Organ Class (SOC) and Preferred Term (PT). Subjects are counted only once under each SOC or PT for which they have at least one TEAE.

Summaries by relationship to study product, by relationship to study procedure and by maximum severity will also be provided.

Serious TEAEs will not be summarized in table format as it is anticipated number of serious TEAEs will be very limited.

In addition, the following AE summaries will be provided for AEs collected at and after rescue visits:

- Overall summary of TEAE
- TEAE by SOC and PT

For these summaries, denominators to be used for percentage calculation will be number of Rescued subjects.

All AEs will be presented in a subject listing with a flag indicating TEAE and a flag indicating AEs occurred at and after rescue visits. In addition, all serious AEs will be presented in a separate listing.

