4.4.1 Potential Risks

Potential risks can be categorized as those risks associated with intraocular surgical procedure and those risks associated with the IMP (AURN001).

Potential Risks Associated with Surgery

Potential risks associated with this intraocular procedure include loss of vision, ocular pain and/or discomfort, ocular hyperemia, dry eye, eyelid edema, increased tearing, subconjunctival hemorrhage, corneal or conjunctival abrasion, corneal ulcer, surgical wound leak, shallowing or collapse of the anterior chamber, Descemet's membrane tear, vitreous prolapse, damage to the iris or other structures, changes to the pupil, intraocular bleeding, infection, endophthalmitis, inflammation (uveitis), worsening of corneal edema, posterior capsular opacification (PCO), worsening of cataract, increased IOP, macular edema (including CME and DME), increase in vitreous opacities, posterior vitreous detachment, and retinal detachment, among others.

Potential Risks Associated with the IMP

Potential risks associated with the IMP (AURN001) include ocular pain and/or discomfort, ocular hyperemia, dry eye, failure to improve corneal edema, corneal ulcer, intraocular inflammation (uveitis), infection, endophthalmitis, increased IOP, graft rejection or failure, changes to the pupil, iris or other structures, posterior capsular opacification (PCO), worsening of cataract, increase in vitreous opacities, and macular edema (including CME and DME) among others. Although tumor formation has not been observed in any animal or clinical studies to date, this is a theoretical risk of receiving any cell therapy.

Previous Experience

In prior clinical trials conducted with AURN001 or an earlier formulation in Japan and El Salvador, the most common risks (>5% occurrence) with both the surgical procedure and IMP were as follows:

First In-Human Clinical Trial (Japan)

- Cystoid macular edema (19%)
- Increased IOP (16%)

Other Clinical Trials (Japan)

- Ocular pain (33%)
- Increased IOP (15%)
- Eyelid edema (7%)
- Increased tearing (7%)

Clinical Trials (El Salvador)

- Posterior capsular opacification (PCO) (29%)
- Pupillary disorder (9%)
- Increased IOP (7%)
- Iris disorder (6%)
- Descemet's membrane tear (6%)

Other less common risks (<5% occurrence) included dry eye, blepharitis, macular edema, and anterior chamber inflammation.

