7.4.2 Collection of Data from Withdrawn Subjects

In the event that study discontinuation of a treated subject is necessary, the investigator should make every attempt to have the subject complete Visit 10 (Month 12) assessments as soon as possible. The reason for premature discontinuation should be recorded in the subject chart and entered in the eCRF.

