10.8 Safety Analyses

All safety analyses will be conducted on the Safety Analysis Set. No formal statistical tests of treatment difference are planned.

AEs will be coded using the Medical Dictionary for Regulatory Activities TEAEs (i.e., AEs that begin or worsen in severity after initiation of study drug) will be summarized by treatment arm and overall, in the study eye. Non-ocular TEAEs will also be summarized. Additionally, TEAEs and serious AEs will be summarized in a similar manner by maximum severity and relationship to study drug and the surgical procedure.

Changes from baseline of quantitative measurements (ophthalmic evaluations, laboratory findings) will be summarized by treatment arm and timepoint.

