4.4 Trial Treatment

Subjects eligible to be treated will receive a single injection of AURN001 (*neltepedocel* with Y-27632), *neltepedocel* alone, or Y-27632 alone into the anterior chamber of the study eye. The dose of *neltepedocel* will be either 1.0×10^6 , 5.0×10^5 or 2.5×10^5 cells; the dose of Y-27632 will be 100 μ M. The total volume of administration will be approximately 300 μ L.

The injection of study treatment into the study eye will be performed under local anesthesia (administration method at the investigator's discretion). After creating a small incision at the corneal limbus, the corneal endothelium will be polished to a diameter of approximately 8 mm. Study treatment will be injected into the anterior chamber using a 27-gauge needle. Immediately after completion of surgery, subjects will lie face down for approximately 3 hours (± 15 minutes).

For detailed instructions, please refer to the Procedure Manual, which includes sponsor observation language.

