5 ANALYSIS SETS

5.1 Full Analysis Set

The Full Analysis Set (FAS) will be defined as all randomized subjects who received any amount of study drug during intracameral injection. All subjects in FAS will be analyzed according to the treatment they actually received. The Full Analysis Set will be the primary population for evaluating all efficacy endpoints, subject characteristics, and protocol deviations.

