5.3 Safety Analysis Set

The Safety Analysis Set will be the same as FAS. The safety analysis set will be the primary population for evaluating treatment administration, concomitant medication and safety.

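### Treatment-emergent AEs and the Safety Set start at the injection, not at the surgery: Day 1 pre-injection complications fall under conflicting rules, and anyone operated on but not injected is in no AE table

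*SAP*

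**What the plan says.** SAP 14.1 defines a TEAE in two limbs. The first is "any adverse events that occur during or after the Day 1 injections". The second covers events already present at screening that worsen from the injection onward. Protocol 10.8 describes "AEs that begin or worsen in severity after initiation of study drug". The AE summaries in SAP 14.1, including those by relationship to product and to procedure, are TEAE summaries. Alongside them are a listing of all AEs with a TEAE flag and a listing of all serious AEs.

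SAP 5.1 defines the FAS as "all randomized subjects who received any amount of study drug during intracameral injection", and SAP 5.3 adds: "The Safety Analysis Set will be the same as FAS". Protocol 10.5 has the same link and also requires that study drug was received.

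SAP 4.4 gives the order of surgery: "After creating a small incision at the corneal limbus, the corneal endothelium will be polished to a diameter of approximately 8 mm". The next sentence is the injection: "Study treatment will be injected into the anterior chamber using a 27-gauge needle".

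Protocol 9.4.1 records AEs from Visit 2 (Day 1), with no restriction to the time after injection. SAP 6.4 defines the start of treatment as a calendar day, and SAP 7.11 works from dates when setting the treatment-emergent flag.

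**The concern.** All five arms have endothelial polishing, so incision and polishing are part of what the protocol does to every subject. Protocol 4.4.1 separates surgical risk from product risk, and its surgical list includes events that can plausibly arise during those steps, such as Descemet's membrane tear, iris damage, vitreous prolapse and intraocular bleeding. The SAP plans a procedure-relatedness table to describe that risk. If the definition starts only at the injection, the table may omit complications from the opening steps of the procedure it describes.

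The Safety Set adds a selection problem. If an intraoperative complication or a product problem stops the operation before the injection, the subject leaves the safety denominator because of what happened in theatre. The sample size is justified partly by characterising safety, so the procedural complication rate is one of the results the trial should report cleanly.

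**Working it through.** The documents state no figure to reproduce, so the check sets the rules side by side for two kinds of subject.

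**Subject A: injected, with a complication that begins during polishing.**

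- SAP 14.1, first limb: onset precedes the injection, so the event does not qualify.
- SAP 14.1, second limb: the event was not continuous from screening, so it does not qualify.
- Protocol 10.8: the event did not begin after study drug. It would qualify only if it later worsened. Protocol 9.4.1 has changes in intensity entered as new records, so a worsening might also be counted under the SAP as a separate event. The literal gap therefore concerns complications that do not worsen after the injection.
- SAP 6.4 and 7.11: study day = event date − treatment start date + 1. For an event dated on the day of surgery this is 0 + 1 = 1, the same as for an event after the injection. Neither document mentions an AE onset time, and neither gives a rule for same-day events that precede the injection. A flag built from dates would probably count the event.

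The written definition excludes this event and the date rules probably include it. The plan does not say which governs.

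**Subject B: surgery started, no injection given.**

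- The subject received no study drug, so is outside the FAS (SAP 5.1) and hence outside the Safety Set (SAP 5.3). No AE table includes the subject, however the TEAE flag is built.
- SAP 5.1 also makes the FAS the population for protocol deviations, so the missed injection is not tabulated there.
- SAP 8 counts the subject among those randomized and untreated, together with anyone who never reached surgery.
- The follow-up request in Protocol 7.4.2 opens with "In the event that study discontinuation of a treated subject is necessary". The section does not define whether Subject B is treated.

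**Scale.** Protocol 4.4.1 gives 6% for Descemet's membrane tear in the El Salvador trials, with no timing relative to injection. The 1% and 2% rows are assumptions for comparison. Expected count = n × p; chance of at least one = 1 − (1 − p)^n.

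| Rate p | Expected, n = 20 | At least one, n = 20 | Expected, n = 100 | At least one, n = 100 |
|---|---|---|---|---|
| 1% | 0.2 | 18% | 1 | 63% |
| 2% | 0.4 | 33% | 2 | 87% |
| 6% | 1.2 | 71% | 6 | 99.8% |

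These are counts of complications, not of events missing from a table. If s is the share beginning before the injection, the literal rule would omit 6 × s of the 6 tears expected in 100 subjects, which is anything from 0 (s = 0) to 6 (s = 1). Under a date-based flag it would omit none among injected subjects. The documents give no value for s.

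The number of subjects like B is also not given. Each would be 1/20 = 5% of a planned arm, or 1/100 = 1% of the planned trial.

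**The case against.** The strongest reply is that the SAP's working rules are date-based and that neither document mentions an AE onset time. Excluding a same-day event would need a clock comparison that the plan does not describe. The documents also treat surgery as part of treatment: polishing is a column in the treatment-assignment table, and the schedule has a single Day 1 line for surgery and study treatment. In practice a Day 1 tear in an injected subject would most likely be tabulated.

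This stands, and it defeats a reading that a reader might infer: that pre-injection complications fall outside every AE table. For injected subjects their inclusion is ambiguous, not ruled out. It also defeats a claim that a 6% tear rate would be reported as 0%. That would need every tear to precede the injection and the literal rule to be applied by clock time, and the documents support neither.

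Nor are the events lost. They are recorded from Day 1 and should appear in the all-AE listing and, if serious, in the serious-AE listing. All arms have the same surgical steps, no formal safety tests are planned, and no between-arm bias is shown. The documents report no case of surgery without injection.

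The reply does not settle two things. A definition that gives the right table only if the programmer departs from its words should be corrected. And the date rules do nothing for a subject outside the Safety Set.

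**Conclusion.** The point holds in two parts of different strength. For injected subjects, the TEAE wording in SAP 14.1 and Protocol 10.8 conflicts with the date rules in SAP 6.4 and 7.11 over complications that begin before the injection on Day 1. The probable outcome in practice is that they are counted. For subjects whose surgery was started but who were not injected, exclusion from the AE tables follows directly from SAP 5.1 and 5.3 and does not depend on how the flag is programmed.

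The size of any undercount cannot be calculated, because both the share of complications before injection and the number of uninjected subjects are unknown. The effect would be on the absolute rate of procedural complications; the documents give no ground for expecting it to differ by arm. It is worth correcting before the Month 6 tables because the remedy is small and the procedure-relatedness table is where the problem would show.

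**What to change.** 1. **TEAE definition (SAP 14.1, Protocol 10.8 and the matching synopsis text).** Define a TEAE as an AE that begins or worsens at or after the start of the Day 1 surgical procedure. An equivalent rule that needs no clock times is to count every AE dated Day 1 that was not present before surgery.
2. **Safety Analysis Set (SAP 5.3, Protocol 10.5).** Define it as all subjects in whom the study procedure was started. Show those not injected in a separate column or row. Placing them under their assigned arm would attribute events to a product they never received and would sit badly with analysis by actual treatment.
3. **Date anchor (SAP 6.4 and 7.11).** Use the date of surgery for uninjected subjects, who have no dosing date.
4. **FAS.** Leave it unchanged for efficacy.

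If only the SAP is revised, SAP 15 should record the change, since it currently declares none.

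The cost is a few lines of text. The Safety Set may differ from the FAS by a few subjects, so some tables will need their own denominators, and reported procedural AE rates may be slightly higher. No new AE collection is needed for Day 1, because Protocol 9.4.1 already starts there.

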14.2 Vision Loss

The number and percentage of subjects who have loss from baseline in BCVA ≥ 15 letters will be summarized using counts and percentages at each post-baseline visit by treatment group and overall.

The best corrected visual acuity will be presented in a listing.

14.3 Rescue Surgery

Rescue surgeries include rescue surgeries given by the investigators even when the rescue criteria were not met.

The number of rescue surgeries will be summarized descriptively by visit. Use of rescue surgeries will be presented in a listing.

Time to rescue surgery is defined as the time duration from Day 1 to rescue date plus 1 for rescue subjects, and from Day 1 to last visit plus 1 for non-rescue subjects.

Medians with 95% CI of time to rescue surgery will be provided and Kaplan-Meier plots will be produced. Time to rescue surgery will be presented in a listing.

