6.5 Trial Duration

An individual subject's participation in the study will last approximately 12 months after injection of study drug. All subjects completing 12-month visit will be invited to participate in a long-term safety study. Data from this study will be reviewed by the Medical Monitor on an ongoing basis in a masked fashion.

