8.3 Rescue Therapy

Subjects whose clinical status declines in the study eye may be evaluated for rescue surgery by Standard of Care Keratoplasty [Descemet membrane endothelial keratoplasty (DMEK), Descemet stripping endothelial keratoplasty (DSEK), or penetrating keratoplasty (PK)].

Consultation with the Medical Monitor is required prior to any procedure. Evaluation will include the subject's visual symptoms, problems, or complaints, and ocular examination findings as available. Subjects who undergo a rescue procedure should be followed for approximately 1 month and may be discontinued from the study thereafter.

All decisions involving rescue surgery should be documented in the eCRF. In addition, all post-rescue follow-up visits should be documented in the eCRF.

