9.3 Disease-Related Events or Outcomes Not Qualifying as AE/SAE’s

Any clinical findings associated with lack of efficacy of the IP are not considered AEs.

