4.2.2 Safety Evaluations

- Incidence and severity of ocular treatment-emergent adverse events (TEAEs)
- Incidence and severity of non-ocular TEAEs
- Loss from baseline in BCVA ≥ 15 letters
- Rescue rate and time to rescue

- Graft rejection

The safety evaluations will be based on adverse event (AE) reporting, laboratory findings (clinical chemistry and hematology), and ophthalmic examinations, including Goldmann tonometry, Slit Lamp biomicroscopy, gonioscopy, dilated fundoscopy, and BCVA (as measured by ETDRS).

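### SAP 14.3 censors every non-rescued subject at the last visit whatever the reason for leaving, so the descriptive time-to-rescue curve can err in either direction if lack-of-effect leavers differ from stayers in later keratoplasty

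*SAP*

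**What the plan says.** SAP 4.2.2 lists "Rescue rate and time to rescue" among the safety evaluations. SAP 14.3 defines two groups only. Rescued subjects have an event at the rescue date. For all others the time runs "and from Day 1 to last visit plus 1 for non-rescue subjects". A subject who completes Month 12 and one who leaves early because the treatment did not work are handled by the same rule. On output, the section states: "Medians with 95% CI of time to rescue surgery will be provided and Kaplan-Meier plots will be produced". No sensitivity analysis is described.

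For a treated subject who leaves early, Protocol 7.4.2 says that "the investigator should make every attempt to have the subject complete Visit 10 (Month 12) assessments as soon as possible", and adds: "The reason for premature discontinuation should be recorded in the subject chart and entered in the eCRF". It asks for nothing later. The other routes by which later surgery might reach the database do not fill the gap:

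- Protocol 9.3: "Any clinical findings associated with lack of efficacy of the IP are not considered AEs".
- Protocol 9.4.1 and 9.4.2: events are recorded through Visit 10, and after discontinuation only SAEs already ongoing are followed.
- Protocol 6.5: "All subjects completing 12-month visit will be invited to participate in a long-term safety study". Subjects who withdrew are not included.

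For subjects rescued on study, Protocol 8.3 says: "Subjects who undergo a rescue procedure should be followed for approximately 1 month and may be discontinued from the study thereafter".

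**The concern.** Kaplan-Meier censoring is harmless when those censored have the same later risk as those who remain. That may fail here. Protocol 7.1 requires that every study eye already needs keratoplasty at entry, so a subject who sees no benefit has an obvious next step. The rescue criteria in Protocol 8.3 speak of clinical decline and require consultation with the Medical Monitor, which does not clearly describe an eye that simply fails to improve. Such a subject might leave and have the operation elsewhere. The plan would then censor that person just when surgery is likely, and nobody would record it.

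At stake is a listed safety evaluation that also speaks to efficacy. In Protocol 4.5 the sponsor cites need for rescue therapy as one sign that cells alone did worse than cells with Y-27632 in an earlier trial. The present trial is meant to assess the contribution of each component, so readers are likely to compare the rescue curves across arms.

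**Working it through.** **Inputs from the documents.** About 20 subjects per arm (Protocol 6.1, SAP 4.1). There is no rescue rate, dropout rate or power figure; SAP 7.3 says the trial is not powered. So there is no planned figure to reproduce.

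**Assumptions.** In one arm of 20, L subjects leave for lack of effect at about day 100. Then r subjects are rescued on study between days 120 and 300. Of the L leavers, m have off-study keratoplasty before Month 12. Everyone else is followed to day 360.

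**Formulas.** All leavers go before the first rescue and nobody else is censored before day 360, so the product-limit estimate reduces to simple ratios at Month 12:

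- planned curve = r / (20 − L)
- truth = (r + m) / 20
- leavers held event-free to Month 12 = r / 20
- leavers counted as events on leaving = (r + L) / 20
- no bias when (r + m)/20 = r/(20 − L), that is m = rL/(20 − L), or m/L = r/(20 − L)

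The last line is the key condition. The planned curve is right when the share of leavers who have surgery equals the share of stayers who are rescued. It is too low above that share and too high below it.

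**Results at Month 12.**

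| r | L | Planned | Leavers event-free | Leavers as events | Break-even m |
|---|---|---|---|---|---|
| 2 | 2 | 2/18 = 11.1% | 10% | 20% | 0.2 |
| 2 | 4 | 2/16 = 12.5% | 10% | 30% | 0.5 |
| 4 | 1 | 4/19 = 21.1% | 20% | 25% | 0.2 |
| 4 | 2 | 4/18 = 22.2% | 20% | 30% | 0.4 |
| 4 | 4 | 4/16 = 25.0% | 20% | 40% | 1 |
| 6 | 4 | 6/16 = 37.5% | 30% | 50% | 1.5 |
| 8 | 4 | 8/16 = 50.0% | 40% | 60% | 2 |

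For r = 4 and L = 4, the truth for m = 0, 1, 2, 3, 4 is 20, 25, 30, 35 and 40%, against a planned 25%. The planned curve is 5 points too high at m = 0, correct at m = 1 and 15 points too low at m = 4. Across the table the largest understatement is 30 − 12.5 = 17.5 points and the largest overstatement is 50 − 40 = 10 points.

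**Median.** With off-study surgery assumed 60 days after leaving, the median moves only when rescue is common. With r = 6 and L = 4 it is not reached under the plan, but is day 300 if all four leavers have surgery. With r = 8 and L = 4 it is day 300 under the plan, day 248 if all four have surgery, and not reached if none do.

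**Difference between arms.** Take the case least favourable to the plan: a constant hazard, a share F needing keratoplasty by Month 12, and a share w of those who leave at that moment and all have surgery. The plotted height is 1 − (1 − F)^(1 − w). At w = 25%, F = 20, 60 and 90% plot as 15.4, 49.7 and 82.2%. A true gap of 60 − 20 = 40 points shows as 34.3, and a true gap of 90 − 60 = 30 points shows as 32.5. Even when every arm is understated, the gap can narrow or widen.

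**The case against.** Censoring at the last visit is the usual rule for a descriptive time-to-event plot. Keratoplasty is offered on study with no time limit, surgery outside the criteria still counts under SAP 14.3, and a rescued subject may leave about a month later. There is little reason to withdraw first, and nothing in the documents shows that anyone would. SAP 8 already summarizes reasons for discontinuation, with disposition presented by arm, and SAP 14.3 lists rescue use and times. No formal safety test is planned (Protocol 10.8). The eCRF is not among the documents, so whether it has a lack-of-effect reason is unknown.

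Most of this stands, and it is why the point is a small one. What it does not remove is that a table of reasons carries no timing and is not linked to the curve, so it cannot show how far the curve depends on these leavers.

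Two stronger readings are tempting and do not hold. A reader might infer that the curve will understate rescue whenever a lack-of-effect leaver has surgery elsewhere. It will not: in the 4-and-4 example one such operation gives no bias, and none gives overstatement. A reader might also infer that the planned curve counts these leavers as rescue-free, and so forms a lower bound beside a composite that counts them all. It does not, because censoring passes on the stayers' risk: the planned 25% and the composite 40% do not contain the 20% that is true if no leaver has surgery.

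**Conclusion.** The point holds as a conditional one. SAP 14.3 ignores the reason for leaving, and neither document collects study-eye keratoplasty after withdrawal. Within an arm, the curve is too low if lack-of-effect leavers have surgery more often than comparable stayers, and too high if less often. In arms of 20 with 1 to 4 such leavers, the illustrated error runs from 17.5 points too low to 10 points too high. Those figures rest on assumed numbers and timing of rescues, exits and off-study operations. With no lack-of-effect leavers there is no error from this source.

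The documents do not support a claim that the comparison between arms is biased in a known direction. Nor do they support a claim that the main result is at risk: under SAP 7.10 and 13.1.1, rescue or dropout before Month 6 counts as failure in the primary analysis. This is a cheap improvement to a descriptive safety output, with medium confidence that it would matter in practice.

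**What to change.** Keep the planned analysis. Add to SAP 14.3 two labelled sensitivity Kaplan-Meier analyses for subjects whose recorded reason for discontinuation is lack of effect:

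1. Count them as events at the discontinuation date (upper bound).
2. Hold them event-free to Month 12 (lower bound).

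State that the planned curve is not itself a bound. Leavers with other reasons keep the planned censoring and lie outside these bounds, which are exact only when nobody else is censored before Month 12. Confirm that the eCRF offers a lack-of-effect reason, and add one if it does not.

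Optionally, add to Protocol 7.4.2 one contact or record check at the planned Month 12 date, where the subject agrees, on whether and when study-eye keratoplasty was done. In the final report, count surgery done by Month 12 at its date in a further sensitivity curve.

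The SAP part can be done alone and costs one or two extra plots. Its weakness is that the first curve mixes withdrawal with surgery, so it must remain a sensitivity analysis. The status check needs a protocol amendment with IRB approval (Protocol 13). Subjects may withdraw without obligation (Protocol 7.4), so some will decline the contact.
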